8.3.1 Visual acuity

Visual acuity will be assessed in the study eye at every study visit and in the fellow eye at the screening and week 52/EOS visits using best correction determined from protocol refraction (BCVA). BCVA measurements will be taken in a sitting position using ETDRS-like visual acuity testing charts at an initial testing distance of 4 meters. The details of the refraction technique and VA testing, as well as training materials, are provided in the applicable manual. Certification of the assessment procedures and assessors will occur prior to any evaluation of study patients.

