1.1 Study design

This study is a 52-week, randomized, open-label, multi-center, two-arm study for pretreated patients with suboptimal anatomically controlled nAMD.

Consenting patients will participate in a screening period, lasting up to 14 days. Eligible patients will be randomized in a 1:1 ratio to one of the two treatment arms:

- Brolucizumab 6 mg “loading arm”: 3 x 4-weekly initial injections followed by an injection every 12 weeks
- Brolucizumab 6 mg “non-loading arm”: one initial injection followed by an injection every 12 weeks

There are three periods in this study (see Figure 1.1):

- Screening period: from day -14 to Baseline
- Open-label treatment period: from Baseline (day 1) to week 48
- Post-treatment follow-up period: from week 48 to week 52

[figure not shown]

Figure 1.1 Study Design

1. Screening period: Day-14 to day -1

A screening period of up to 2 weeks will be used to assess eligibility.

One time rescreening of patients is allowed, except for the purpose of capturing new BCVA or imaging assessments that previously failed to qualify the patient. As long as testing can be repeated within 14 days of the first screening, the other screening assessments do not need to be repeated. If rescreening is to occur beyond 14 days from the original screening visit date, then all screening procedures must be repeated. Medical judgment should be exercised to ensure that treatment of nAMD is not withheld in order for a patient to participate in the study.

2. Open-label treatment period: Day 1 to Week 48

After confirmation of eligibility, patients will be randomized in a 1:1 ratio to one of the treatment arms.

Only one eye will be selected as study eye and treated with study medication.

The baseline visit is defined as Day 1/Visit 1, and end of treatment visit as Visit 13 (Week 48).

A study visit schedule will be established at the time of randomization for all patients with study visits scheduled every 4 weeks. All efforts should be made to adhere to this study visit schedule ± 7 day window. Treatment is intended to be administered on the day of study visit, or if this is not possible, within 3 days after the study visit when the per-protocol assessments took place. In addition, for a given protocol visit, assessments can be performed on two consecutive days.

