2.2 Analysis sets

The **Randomized Set** (RAS) consists of all randomized patients.

The **Full Analysis Set** (FAS) comprises all subjects who receive at least one IVT injection of the study treatment. The FAS will serve as the primary analysis set for all efficacy analyses. According to the intent to treat principle, subjects will be analyzed according to the treatment they have been assigned to during the randomization procedure.

The **Safety Set** includes all subjects who received at least one dose of study treatment. Subjects will be analyzed according to the study treatment received, where treatment received is defined as the actual treatment regime. If the subject took only one dose of study treatment, the subject will be analysed according to the randomized treatment regime.

Relevant protocol deviations and their potential impact on the analysis will be assessed and adequately documented / processed before database lock.

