2.5.2 Statistical hypothesis, model, and method of analysis

The analysis of the primary endpoint will be performed in a purely descriptive manner and non-inferiority testing will be omitted. To evaluate the outcome in terms of mean change in BCVA from baseline to mean of visits at week 40 through week 52, a two-sided 95% confidence interval for the treatment difference will be derived from a mixed model with repeated measures (MMRM) model with factors treatment arm, baseline BCVA and age. An unstructured

covariance structure shared across treatment arms was used to model the within-patient errors. Programming details are specified in section 5.4.

The FAS will be used to analyze the primary endpoint.

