5.4 Statistical models

5.4.1 Primary analysis

1) SAS-Code for **mixed model for repeated measures (MMRM)**:

Estimates for the primary objective ("Mean change in BCVA from baseline to mean of visits at week 40 to week 52 (Visit 11 to 14)") and the secondary objective ("Mean change in BCVA from baseline to mean of visits at week 16 to week 28 (Visit 5 to 8)") in one single model:

```
proc mixed alpha=0.1;
  where fasfl=Y and trteyen=1;
  where 2 le avisitn le 14;
  class subjid trtan avisitn;
  model chg = base age trtan avisitn trtan*avisitn /ddfm=kr;
  repeated avisitn / sub = subjid type = un;
  lsmeans trtan*avisitn /slice = avisitn cl ;
  estimate 'Treatment difference averaged over week 40 to week 52'
    trtan -1 1
    trtan * avisitn
      0 0 0 0 0 0 0 0 -0.25 -0.25 -0.25 -0.25
      0 0 0 0 0 0 0 0 0.25 0.25 0.25 0.25/cl;
  estimate 'Treatment difference averaged over week 16 to week 28'
    trtan -1 1
    trtan * avisitn
      0 0 0 -0.25 -0.25 -0.25 -0.25 0 0 0 0 0 0
      0 0 0 0.25 0.25 0.25 0.25 0 0 0 0 0 0/cl;
run;
```

3) SAS-Code for **logistic regression** model:

- Secondary endpoint: "rate of patients (overall and per treatment arm) with prolonged interval (*intlong*) compared to mean treatment interval in last 24 weeks prior to enrollment"

```
proc logistic descending alpha=0.05;
  where fasfl=Y;
  class trtan;
  model intlong = base age trtan;
run;
```

- Secondary endpoint: "proportions of patients maintained at a q12w interval from baseline / upload to week 52"

```
proc logistic descending alpha=0.05;
  where fasfl=Y;
  class trtan;
  model q12w = base age trtan;
run;
```

where 'maintained at a q12w interval' (q12w = Yes) is defined as DAA = q12w in all visits AND no treatment discontinuation.

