5.5 Rule of exclusion criteria of analysis sets

Table 1 Protocol deviations that cause subjects to be excluded

Deviation ID	Description of Deviation	Exclusion from Analyses
I_01	No written informed consent	Excluded from all analyses
D_00	Not treated with any study medication	Excluded from FAS and SAF
O_VI0	No Post-baseline visit performed	Excluded from FAS

Table 2 Subject Classification

Analysis Set	PD ID that cause subjects to be excluded	Non-PD criteria that cause subjects to be excluded
ENR	I_01	
RAN	I_01	Not randomized
FAS	I_01, D_00, O_VI0	Not in RAN
SAF	I_01, D_00	

6 Reference

Not applicable.

7 Declaration of sponsor and clinical research organisation

Declaration by client:

[figure not shown]
This statistical analysis plan has been approved after review by

Client:

Digitally signed by [REDACTED]
DN: dc=com, dc=novartis, ou=people,
ou=PH, serialNumber=3168921,
cn=[REDACTED]
Reason: I am approving this document
Date: 2024.04.03 21:12:12 +02'00'

Date

Digitally signed by [REDACTED]
DN: dc=com, dc=novartis, ou=people,
ou=PH, serialNumber=1451277,
cn=[REDACTED]
Reason: I am approving this document
Date: 2024.04.03 11:20:21 +02'00'

[figure not shown]
Date

Declaration of clinical research organisation:

[figure not shown]
This statistical analysis was prepared based on the clinical study protocol (Amended Clinical Study Protocol, version 02 dated 03-NOV-2022) by

[REDACTED] :

Date

[REDACTED] (CRO Biometrician)

Date

[REDACTED] (CRO Biometrician)

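### The primary PROC MIXED code in SAP 5.4.1 has two plain WHERE statements; the second replaces the first, so the full-analysis-set and eye filters are not applied (minor, data-dependent, free to correct)

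*SAP*

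**What the plan says.** SAP 2.5.2 fixes the population for the primary endpoint ("The FAS will be used to analyze the primary endpoint") and refers the reader to SAP 5.4 for programming details. The code printed there is therefore part of the specification.

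The PROC MIXED step in SAP 5.4.1 contains, as two separate statements, "where fasfl=Y and trteyen=1" and "where 2 le avisitn le 14". The within-patient structure is "repeated avisitn / sub = subjid type = un". The step names no input dataset.

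The FAS "comprises all subjects who receive at least one IVT injection of the study treatment" (SAP 2.2). SAP 5.5 also removes patients from it for "No Post-baseline visit performed".

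On eyes, SAP 1.1 states: "Only one eye will be selected as study eye and treated with study medication". Protocol 8.3.1 has acuity measured in the study eye at every visit, and also "in the fellow eye at the screening and week 52/EOS visits using best correction determined from protocol refraction (BCVA"). SAP 2.1.1 defines the baseline visit as day 1 (Visit 1). SAP 2.5.1 to 2.5.3, the text of the primary analysis, does not mention the study eye. The table of secondary endpoints in SAP 2.7.2 does, for the by-visit acuity summaries.

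**The concern.** Within one SAS procedure step, WHERE conditions accumulate only if they are joined by AND or added with WHERE ALSO or WHERE SAME AND. A second plain WHERE overwrites the first and leaves only a note in the log. Read this way, the printed step selects visits 2 to 14 and nothing else.

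The eye filter matters more than the FAS flag. The FAS is also stated in the prose, whereas the overwritten line is the only place where the primary-analysis specification restricts records by eye. Fellow-eye acuity is collected at week 52 (Visit 14), one of the four visits that make up the primary endpoint. At stake is whether the model that produces the primary result runs at all on a two-eye dataset and, if it does, whether it uses only the treated eye.

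**Working it through.** **Planning figures.** The point does not rest on them, and the fix leaves them unchanged. The stated half-widths reproduce: 1.96 × 13 × √(2/25) = 7.21 letters and 1.96 × 13 × √(2/23) = 7.51 letters (SAP section 3).

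**Which filter is active.** The last WHERE statement in the step is the visit range, so the active subset is visits 2 to 14. The conditions on `fasfl` and `trteyen` do not apply. Each PROC LOGISTIC step has one WHERE statement and does not share this fault.

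**Losing the FAS flag.** Take the reasons in SAP 5.5 for being outside the FAS in turn:
- No consent: excluded from all analyses anyway.
- No post-baseline visit: contributes no record at visits 2 to 14.
- Not treated: could enter only if randomised, never injected, and still measured for acuity after baseline.

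The last is the only route in, and it is narrow.

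**Losing the eye filter.** The outcome depends on how fellow-eye change is derived, which the SAP does not say.

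1. *Baseline is day 1 for both eyes.* Fellow-eye acuity is not scheduled on day 1, so the fellow eye has no baseline and no change value. PROC MIXED drops records with a missing response or covariate. Effect: none.

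2. *Screening serves as the fellow-eye baseline.* The fellow eye then has a change value at Visit 14.
 - Study-eye rows: at most 13 visits × 50 patients = 650 (13 × 46 = 598 for 23 per arm).
 - Fellow-eye rows added: at most 50 (or 46), all at Visit 14.
 - Share of Visit 14 rows: at most 50/(50 + 50) = 1/2.
 - Share of week 40 to 52 rows: at most 50/(4 × 50 + 50) = 1/5.

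 A patient with both eyes at Visit 14 has two records at the same level of the repeated effect. Under the unstructured covariance, the 13-visit matrix with its last visit duplicated is 14 × 14 but has rank 13. It is singular, the likelihood is undefined, and the fit stops.

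3. *As in 2, but the study-eye Visit 14 value is missing.* That patient has no duplicate, so the fellow-eye value can be used as if it were the study eye. This goes unnoticed only if no other patient's duplicate stops the run, or if duplicates were removed by patient and visit without regard to eye.

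**Unquoted flag.** `Y` has no quotation marks, so SAS would look for a variable of that name and report an error. Once that is corrected, the WHERE replacement remains and produces only the log note.

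**The case against.** The strongest reply is that no harm follows from the SAP's own definitions. Baseline is day 1, the fellow eye is not scheduled for acuity that day, and no SAP endpoint needs a fellow-eye change. This carries weight: it makes the harmless case a natural reading. It does not settle the matter, because the SAP neither says how fellow-eye change is derived nor says that the input data are already limited to the study eye. The presence of an eye filter suggests that its authors expected both eyes in the data.

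It can also be said that the code is a sketch. It names no dataset and has unquoted flags, so it must be edited before it runs, and the intended population is clear from the prose and from the first WHERE line. That is fair. This is a slip in a programming specification and not a change of planned population. Duplicate records would stop the fit visibly and would not bias it silently.

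A reader might infer a measurable bias: week 52 has weight 0.25, half of its rows could be fellow eyes, so the contrast is diluted by 0.25 × 0.5 = 12.5%. The documents do not support this. It needs a screening baseline for the fellow eye, a fit forced through despite the duplicates, and no arm effect in fellow eyes. It also needs Visit 14 to carry that weight. The first ESTIMATE statement prints 12 interaction coefficients per arm for 13 visits; read in sequence, they fall on visits 10 to 13 in one arm and 9 to 12 in the other, leaving Visit 14 with zero weight. That is a separate fault, but it removes the basis for the figure.

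**Conclusion.** The code as printed does not apply the FAS and eye restrictions, and so does not implement SAP 2.5.2. That follows from how SAS treats repeated WHERE statements and needs no assumption about the data, beyond correcting the unquoted flag.

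The consequence is conditional. There is none if fellow-eye change is missing. There is a failed fit if screening is the fellow-eye baseline and both eyes have Visit 14 values. An occasional wrong-eye value is possible where the study-eye Visit 14 value is missing. Dropping the FAS flag alone matters little. No dilution or bias figure can be given, and the row counts above are ceilings under the second scenario. That `trteyen=1` marks the study eye is inferred from its name, since the SAP does not define it.

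A reader might take this as a defect that invalidates the primary result. The documents do not support that: the analysis is descriptive, the intended population is stated, and the likeliest harmful case would be seen at once. It is a minor correction to the primary-analysis code.

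**What to change.** Replace the two statements in SAP 5.4.1 with one:

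`where fasfl='Y' and trteyen=1 and 2 le avisitn le 14;`

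Put quotation marks round the flag value in the two PROC LOGISTIC calls as well. Before fitting, check that each combination of `subjid` and `avisitn` occurs once. It would also help to define `trteyen` and to say in SAP 2.5 that the primary endpoint is measured in the study eye.

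The cost is one line of code, two pairs of quotation marks and a routine data check. The estimand, the planned population and the precision figures do not change.

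### The primary ESTIMATE statement has 12 interaction coefficients per arm for a 13-visit model, so as written it cannot give the week 40 to 52 treatment difference

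*SAP*

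**What the plan says.** SAP 2.5.2 takes the primary estimate from an MMRM and hands over the detail: "Programming details are specified in section 5.4". Section 5.4.1 states the target as "Mean change in BCVA from baseline to mean of visits at week 40 to week 52 (Visit 11 to 14").

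The parts of the code that matter are:

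- Visits kept: "where 2 le avisitn le 14".
- Class order: "class subjid trtan avisitn".
- Model: "model chg = base age trtan avisitn trtan*avisitn /ddfm=kr".
- Primary contrast, first interaction row: "0 0 0 0 0 0 0 0 -0.25 -0.25 -0.25 -0.25".
- Primary contrast, second interaction row: "0 0 0 0 0 0 0 0 0.25 0.25 0.25 0.25/cl".
- Week 16 to 28 contrast, first interaction row: "0 0 0 -0.25 -0.25 -0.25 -0.25 0 0 0 0 0 0".

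The visit restriction stands in a WHERE statement of its own, after a separate WHERE statement that selects the FAS and the study eye.

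**The concern.** The two contrasts belong to the same model, so their interaction rows must have the same length. They do not: the primary rows are one entry shorter than the week 16 to 28 rows. An ESTIMATE statement has no visit labels and assigns coefficients purely by position, so one missing entry moves every weight that follows it.

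This statement produces the trial's primary result. The averaging window was also chosen for a reason. Protocol 4.1 explains that patients on q12w may have their last injection at week 44 in the loading arm and week 48 in the non-loading arm, and that averaging four time points is meant to reduce the resulting bias. A contrast that drops week 52, or sets the two arms four weeks apart, defeats that purpose.

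**Working it through.** **Inputs**

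- Visit 1 is baseline (SAP 2.1.1). Visits are every 4 weeks and visit 13 is week 48 (Protocol section 3). Hence week = 4 × (visit − 1).
- Model visits 2 to 14: 14 − 2 + 1 = 13 levels, weeks 4 to 52.
- With `trtan` before `avisitn` in CLASS, the interaction has 2 × 13 = 26 columns. Columns 1–13 belong to arm level 1 and columns 14–26 to arm level 2. Within an arm, visit = position + 1.
- Standard SAS behaviour, not stated in the documents: coefficients are read in sequence across line breaks, and omitted trailing ones are zero.

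**Target.** Visit 11 is week 4 × 10 = 40 and visit 14 is week 4 × 13 = 52, as the SAP says. The weights must therefore stand at positions 10–13 of each arm, after nine zeros.

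**Control: the week 16 to 28 contrast.** 3 zeros + 4 weights + 6 zeros = 13 per arm, 26 in all. The weights stand at positions 4–7, which are visits 5–8, weeks 16–28, in both arms. This reproduces its label and confirms that 13 is the required length.

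**Primary contrast as printed.** 8 zeros + 4 weights = 12 per arm, 24 in all for 26 columns.

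| Row | List positions of the weights | Arm level | Visits | Weeks |
|---|---|---|---|---|
| First (−0.25) | 9–12 | 1 | 10–13 | 36, 40, 44, 48 |
| Second (+0.25) | 12 + 9 to 12 + 12 = 21–24, i.e. 8–11 within the arm | 2 | 9–12 | 32, 36, 40, 44 |

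Week 52 has weight 0 in both arms, and arm level 2 also omits week 48.

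**Estimability.** Each interaction column is non-zero in one arm-by-visit cell only. The coefficients on the lower-order terms must therefore equal the sums of the interaction weights.

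- Arm: sums are 4 × (−0.25) = −1 and 4 × 0.25 = +1. These match the treatment coefficients −1 and 1.
- Visit: visit 9 sums to 0 + 0.25 = +0.25. Visits 10, 11 and 12 each sum to −0.25 + 0.25 = 0. Visit 13 sums to −0.25 + 0 = −0.25. The statement gives no visit coefficients, so 0 is supplied where +0.25 and −0.25 are needed.

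The contrast is therefore not estimable. A numerical check agrees. With X = intercept, baseline, age, 2 arm, 13 visit and 26 interaction columns, the test is whether L·X⁺X = L, where X⁺ is the pseudo-inverse of X.

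| Contrast | Largest deviation | Weeks weighted |
|---|---|---|
| Week 16 to 28, as printed | 0 (estimable) | 16–28, both arms |
| Primary, as printed | 0.083 (not estimable) | 36–48 against 32–44 |
| Primary, each row padded at its end | 0 (estimable) | 36–48, both arms |
| Primary, one leading zero added per row | 0 (estimable) | 40–52, both arms |

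The 0.083 shows only that the contrast is not estimable. It is not a bias in letters. The comparison of weeks 36–48 with weeks 32–44 would become a number only if visit coefficients, absent from the SAP, were added.

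**WHERE statements.** In SAS a second WHERE statement in the same step replaces the first, so the FAS and study-eye selection would be lost. Protocol 8.3.1 collects fellow-eye BCVA at screening and at week 52/EOS. The exposed visit is therefore visit 14, which lies inside the primary window.

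**The case against.** Four points can be made for the plan.

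- **The missing zero may be a PDF reading fault.** It is missing from the longest run of identical characters in the code, where such a loss is most likely. This cannot be fully excluded. But both primary rows lack exactly one zero and both week 16 to 28 rows are complete, which points to the SAP itself. A look at the signed file settles it.
- **The failure would show itself.** This stands. The stated model should return a non-estimable result, not a plausible wrong number, so a programmer would probably notice at the first run. That lowers the risk of a silent error. It also means the repair would be made once outcome data are in hand and outside the approved plan.
- **The target is unambiguous.** Protocol 12.4 and SAP 1.2, 2.5.1 and 2.5.2 all give weeks 40 to 52, the contrast carries that label, and the LS means by arm and visit are requested. All true, and it makes the correct repair certain. It does not make the code right, and SAP 2.5.2 relies on that code.
- **The analysis is descriptive, and the WHERE effect is unproven.** No decision rule depends on the contrast, but the primary estimate and its interval must still be computable as specified. The effect of the lost study-eye filter does depend on whether the input dataset holds fellow-eye rows. The filter suggests so; the documents do not say. Losing the FAS filter would matter little, since SAP 5.5 excludes few subjects and those without a post-baseline visit have no rows at visits 2 to 14.

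**Conclusion.** The point holds. The primary ESTIMATE statement has 24 interaction coefficients where the model has 26 columns. As printed it is not an estimable function of the stated model. By position it weights weeks 36–48 in one arm and weeks 32–44 in the other, and never week 52. Even the kindest reading, padding each row at its end, averages weeks 36–48. So no reading of the printed code yields the defined primary endpoint.

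This rests on standard SAS handling of coefficient order, omitted coefficients and repeated WHERE statements, and on the printed code matching the signed SAP. The coding of the treatment variable is not given, so the arms cannot be named. The WHERE problem is secondary, and the coefficient error stands without it. The correction should be made before the primary analysis is run, or documented as a correction to the SAP if it has been.

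**What to change.** In SAP 5.4.1:

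1. Put one more zero at the front of each interaction row of the primary ESTIMATE. Each row then has nine zeros followed by the four weights: −0.25 in the first row, 0.25 in the second. The count is 9 + 4 = 13 per arm.
2. Combine the FAS, study-eye and visit 2 to 14 conditions in a single WHERE statement.
3. Add a check that the estimate equals the simple average of the four visit-specific LS-mean differences at weeks 40, 44, 48 and 52.

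The cost is two added zeros, one merged line and one check, recorded as a correction to the SAP. No data, endpoint or protocol text changes.

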Brolucizumab has been approved for treatment of nAMD by more than 70 health authorities globally, e.g. the Food and Drug Administration (FDA), the European Medicines Agency (EMA) and Swissmedic. It was tested in two large phase 3 trials and found to be efficacious and safe when compared to aflibercept in patients with nAMD (HAWK and HARRIER). Brolucizumab demonstrated non-inferiority to aflibercept in mean change in best-corrected visual acuity (BCVA) from baseline to week 48 in both trials. Treatment of treatment-naïve patients was started with three monthly brolucizumab injections (loading phase), followed by treatment every 12 weeks (q12w). If disease activity was identified during the study, patients were assigned to treatment every 8 weeks (q8w) and stayed on the q8w interval until the end of study. After one year of treatment, the primary endpoint was met with change of BCVA from baseline being non-inferior with more than 50 % of patients (56 % in HAWK, 51 % in HARRIER) were being maintained on a q12w dosing interval following the loading phase through week 48 in the brolucizumab arm vs. the aflibercept arm (fixed q8w treatment frequency). The visual acuity gains observed in the first year were maintained in the second

year. In addition, in these phase 3 trials brolucizumab demonstrated superior anatomical outcomes vs. aflibercept. Significantly fewer patients on brolucizumab had intraretinal fluid (IRF) and/or subretinal fluid (SRF) and brolucizumab achieved superior reductions in central subfield thickness (CSFT) versus aflibercept. These superior anatomic outcomes for brolucizumab were maintained in the second year. Brolucizumab safety was comparable to aflibercept, with the overall incidence of adverse events balanced across all treatment groups in both studies.

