2.7.2 Statistical hypothesis, model, and method of analysis

Secondary endpoints will be analyzed using adequate descriptive statistics, if not otherwise specified. Details on planned analyses are listed in the table below.

Table 2 Endpoints and statistical method

Endpoints for secondary objectives	Statistical method
1.Treatment interval	
1.1. Mean treatment interval (overall as well as per study group comparing treatment intervals from week 8 to week 52 in the study vs. 24 weeks to baseline prior to enrollment)	Descriptive analysis of injection intervals (weeks): Summary statistics (n,mean, SD, min, median, max) for - Mean treatment interval from week 8 to week 52 - Mean treatment interval within 24 weeks prior to baseline. - Last treatment interval under observation Box Plot for “last treatment interval under observation”. Stacked Bar Chart for patients on q8w and q12w by visit (last documented DAA).

1.2. Rate of patients (overall and per group) with prolonged interval compared to mean treatment interval in last 24 weeks to baseline prior to enrollment

- **Frequencies and percentages (n(%))** for total FAS and both treatment arms.

- **Logistic regression model**

Dependent variable: interval prolongation* (Y/N)

Factors:

- treatment arm
- baseline BCVA
- age

Odds-ratio, 95% CI and p-value.

Estimates for , non-loading arm, loading arm and difference (non-loading – loading).

* Prolongation is calculated by comparing the “mean treatment interval in last 24 weeks prior to first brolucizumab injection” (defined in section 2.3.2) with the time interval between the last two brolucizumab injections. Patients with only one injection in treatment period are calculated as non-responders (no interval prolongation).

2. Maintenance of q12w intervals

2.1. Comparison of proportions of patients maintained at a q12w interval at week 52 between the two arms

- **Frequencies and percentages (n(%))** for total FAS and both treatment arms.

- **Logistic regression model**

Dependent variable: “q12w” (Yes/No): “DAA maintained at q12w from baseline / upload to week 52”

Factors:

- treatment arm
- baseline BCVA
- age

Odds-ratio with 95% CI and p-value.

Patients who discontinued treatment prior to week 52 are calculated as non-responders.

2.2. Distributions of patients at q8w/q12w intervals from baseline to week 52

Descriptive statistics for treatment regimens:
Frequencies and percentages (n (%)) by visit

3. Functional Outcomes

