2.14 Interim analysis

There is no interim analysis planned.

3 Sample size calculation

Due to feasibility reasons, resulting in a substantial delay in recruitment, as described above, with Amendment 2 the recruitment will be prematurely discontinued. A final number of approximately 50 patients is expected to be recruited by the time of approval of the amendment.

As a consequence, all analyses will be performed and interpreted in a purely descriptive manner.

Based on an expected sample size of 25 patients per group, and an assumed common standard deviation of 13 letters, a precision in terms of the width of the respective 95% confidence interval for the difference in change from baseline of the visual acuity of +/- 7,21 can be achieved. Taking into account the current number of patients of (for 23 patients per group), the precision in terms of the half width of the 95% confidence interval would be 7,51.

4 Change to protocol specified analyses

The wording of secondary objective 2) was slightly changed to: "Comparison of proportions of patients maintained at a q12w interval **from baseline / upload to week 52**" instead of per protocol: "Comparison of proportions of patients maintained at a q12w interval **at week 52**".

5 Appendix

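### Firth's penalised likelihood would be a cheap, low-severity improvement on the plain logistic regression planned for the two binary interval endpoints in about 46 to 50 patients

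*SAP*

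**What the plan says.** SAP Section 5.4.1 gives the code for both binary secondary endpoints. Each call opens with "proc logistic descending alpha=0.05". The model statements are "model intlong = base age trtan" for interval prolongation and "model q12w = base age trtan" for q12w maintenance. Neither carries a penalised or exact option, and the SAP does not say what is reported if the fit has no finite solution.

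SAP Section 2.7.2 (Table 2) asks for "Odds-ratio, 95% CI and p-value" for prolongation, and for the same three quantities for q12w maintenance. For both endpoints it also asks for frequencies and percentages, overall and per arm. Protocol Section 12.5.1 says that logistic regression will be used for these two endpoints but names no covariates.

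The sample size is in SAP Section 3: "Based on an expected sample size of 25 patients per group, and an assumed common standard deviation of 13 letters", and then "Taking into account the current number of patients of (for 23 patients per group), the precision in terms of the half width". Allocation is 1:1. All analyses are described as descriptive. No expected event rate is stated for either endpoint in this trial. The nearest figure is in Protocol Section 1.1, the share kept on q12w in two earlier phase 3 trials in treatment-naive patients: "56 % in HAWK, 51 % in HARRIER".

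**The concern.** With 46 to 50 patients and a model of arm plus two adjusters, two small-sample properties of ordinary ML logistic regression matter.

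- **Bias.** When a real effect exists, the log odds ratio is on average too far from zero.
- **Separation.** If nearly all patients share one outcome, an arm may contain no patient with the other. The estimate then does not exist, and the analyst must choose another method after seeing the data, in an open-label trial.

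These odds ratios are the only modelled results on whether patients without loading extend or hold their interval. Because the trial no longer tests a hypothesis, the point estimate and its interval are what readers will take away. An estimator with less bias and less error is therefore worth having if it is nearly free.

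**Working it through.** **1. Inputs from the documents.** 25 per arm (50 in total) or 23 per arm (46 in total); 1:1 allocation; terms for arm, baseline BCVA and age; two-sided 95% intervals. The only q12w rates are 51 and 56%.

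**2. The plan's own precision figure.** SAP Section 3 gives a half-width for the BCVA difference: 1.96 × 13 × √(2/n).
- n = 25: 1.96 × 13 × 0.2828 = 7.21 letters, as stated.
- n = 23: 1.96 × 13 × 0.2949 = 7.51 letters, as stated.

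The sample-size inputs are thus read correctly. The documents give no such figure for the logistic models.

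**3. Inputs that had to be assumed.** Event rates, true odds ratios and covariate effects. The SAP model was simulated and each data set was fitted by ML and by Firth's method. Separation means that no finite ML estimate exists.

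**4. A worked case.** 23 per arm, true OR 2 (log OR 0.69), covariate coefficients 0.35 and -0.25 per SD, 3000 data sets per cell:

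| Event rate | Mean log OR, ML | Mean log OR, Firth | RMSE, ML | RMSE, Firth | Reduction |
|---|---|---|---|---|---|
| 50% | 0.77 | 0.70 | 0.71 | 0.63 | 11% |
| 65% | 0.79 | 0.71 | 0.77 | 0.68 | 12% |
| 80% | 0.76 | 0.69 | 0.93 | 0.83 | 11% |

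At 50%, exp(0.77) = 2.16 against a true 2, and Firth gives exp(0.70) = 2.01. The ML bias is 0.77 - 0.69 = 0.08. The sampling SD is √(0.71² - 0.08²) = 0.71, so the bias is about 11% of one SD. Squared bias is 0.0064 of a mean squared error of 0.504, or about 1%. Most of the error reduction therefore comes from lower variance, not from removing the bias.

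**5. Wider range for the bias.** At overall rates of 20 to 80%, the geometric-mean ML odds ratio was about 2.1 to 2.2 for a true 2 and 3.1 to 3.5 for a true 3. Firth gave about 2.0 and 2.9 to 3.1. At reference-arm rates of 51 to 56%, a true 0.5 gave 0.46 to 0.47 with ML and 0.50 to 0.51 with Firth. A true 1 gave 0.99 to 1.01 with either. In all, ML lies about 4 to 17% further from 1 when an effect exists.

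**6. Error and coverage.** RMSE fell by about 3 to 15% over rates of 20 to 80%, and by 8 to 15% at 35 to 65%. ML Wald coverage was about 94 to 97% at 20 to 80%. Firth Wald coverage was 96 to 97% at 51 to 56%.

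**7. Separation.** By overall rate it was about 1 to 6% at 20% or 80% and about 13 to 30% at 90%. At reference-arm rates of 51 to 56% it was 0 to 0.3%. The definition of the rate matters. With a reference-arm rate of 80% and OR 3, the odds in the other arm are 4 × 3 = 12, a rate of 12/13 = 92%, so the overall rate is about 86%. Ranges indexed by the reference arm are therefore wider (0.2 to 15% at 80%).

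**8. The sparse end.** At 90% the ML fits that exist tend to fall below the truth, and Firth shrinks further. With reference rate 90%, true OR 2 and N = 46, ML gave 1.56 to 1.96 and Firth 1.39 to 1.63. On the same data sets Firth's RMSE at 90% was still 15 to 26% lower. If Firth is scored on all data sets and ML only on those where it exists, there is no gain.

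**The case against.** The strongest reply is that nothing here is wrong. Logistic regression is a standard method and its intervals cover at about the nominal rate. In the worked case an approximate interval around the average ML estimate is exp(0.77 ± 1.96 × 0.71), about 0.5 to 8.7. No reader would conclude differently because the centre is 2.16 and not 2.01. The endpoints are secondary and descriptive, and crude counts per arm stand beside each odds ratio, so an unstable estimate would be visible. All of this stands, and it sets the severity.

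Firth also has a cost. At a 10% reference rate and a true OR of 0.5, in data sets where ML exists, Firth gives 0.69 to 0.70 and ML 0.61 to 0.62. Firth is then further from the truth.

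Three stronger readings are tempting, and the documents do not support them:

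- *Separation is a general hazard at this sample size.* It depends on the event rate, which the documents do not give, and it is practically absent at 51 to 56%. Prolongation could be common, because prior intervals may be as short as q4w while study intervals after initiation are at least 8 weeks. But entry extends to q12w, and patients with a single injection count as not prolonged. A high rate is an inference.
- *ML always overstates.* It does not at OR 1, nor reliably at very sparse rates.
- *The model was designed for 490 patients and carried over.* The documents do not show the pre-amendment analysis text. The covariates appear in a SAP based on Amendment 2.

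**Conclusion.** This is a cheap improvement of low severity, not an error in the plan. At event rates of about 20 to 80% the planned odds ratios would lie roughly 4 to 17% too far from 1 if an effect exists. That is small against a sampling SD of about 0.7 or more on the log scale. Firth's method removes nearly all of this bias and lowers the error by about 8 to 15% at rates of 35 to 65%. It also gives a finite estimate whenever both outcomes occur, which closes the gap left by the missing separation rule. The sizes rest on assumed event rates, odds ratios and covariate effects. The direction of the RMSE result was the same in every scenario when both methods were scored on the same data sets.

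**What to change.** In SAP Section 5.4.1, add `/ firth clodds=pl` to both model statements and report profile penalised-likelihood confidence intervals. Name the method in Section 2.7.2 and keep the crude n (%) per arm as planned. If the sponsor prefers to keep ML as the main fit, the minimum is to name Firth or an exact method in advance as the fallback when separation is detected.

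The cost is one option per model and a sentence in the report; no new data are needed. The downsides are slight shrinkage of predicted probabilities toward 0.5 (and of the odds ratio toward 1, most visibly when one outcome is rare), slightly conservative intervals, and a less familiar estimator to describe. The option syntax is software knowledge and cannot be checked in the documents.
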